The current research can be classified as a feasibility/effectiveness design . First we will document the feasibility of community based implementation of an evidence-based 12-session Group Lifestyle Balance (GLB-12) intervention among retirees and/or their dependent spouses/partners who have enrolled or are about to enroll in Medicare benefits through the University of Pittsburgh. We will also recruit from other community locations. Following implementation of the non-randomized GLB-12, participants will be assigned by a stratified block randomization scheme to continued telephone contact (GLB + 8TC; N = 160) or to newsletter control (GLB + NC; N = 160) for the remainder of the one year intervention. Stratification will be based on the category of percent weight loss achieved during the first phase of intervention (<3.5 % and >3.5%). Major outcome assessments will be conducted at 0, 4, 12 and 24 months.

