All analyses will be conducted in consultation with [name], the study biostatistician. Descriptive analyses and graphic displays will be used to identify outliers, missing data and patterns of attrition that will guide decisions about the use of transformations and appropriate tests. Demographic variables and baseline measures will be compared between the GLB+10TC and GLB+NC conditions. In all outcome analyses we will use an intent-to-treat (ITT) approach in which participants remain in the study arm to which they are randomized regardless of attrition. The primary analytic strategy will be a mixed models approach in which treatment group, time, and time by group interaction are treated as fixed effects, and subject and percent weight loss during the first phase of intervention (<3.5% and >3.5%) are treated as a random effects to account for individual subject variability. Hypothesis tests will be two-sided and significance will be set at the 0.05 level. Analytical tools will include SAS (SAS Institute, Inc., Cary NC), Stata (StatCorp LP, College Station, TX) and StatXact (Cytel, Inc. Cambridge, MA). Mixed models are applicable to longitudinal datasets that contain missing observations, with

the assumption that the data are considered to be missing at random (MAR) or ignorable missing. Although we will be proactive in maximizing subject retention, we anticipate 75% adherence over the 12-month intervention period. Those who drop out or are lost to follow-up will be compared to those who have completed intervention sessions and research assessments using standard parametric and non-parametric methods, as appropriate. We will examine the patterns of missingness and, if necessary, account for missingness in outcome analysis (e.g., the covariate approach). Finally, regression modeling will be conducted to adjust for covariates, including demographic variables such as age, race, sex, number of sessions completed, as well as any other variables that have been found to differ across treatment conditions at baseline.

Research Questions

Hypothesis 1 (feasibility): On average, we will enroll ≥ 107 participants per year for each of three years to GLB-12; they will complete $> 65\%$ of sessions, return $\geq 50\%$ of self-monitoring records and report above average program satisfaction at the 4-month assessment.

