Analysis Plan: We will compare GLB + 10TC and GLB + NC on changes in absolute and percent weight loss and each of the other outcome measures with a repeated measures mixed model. To test the treatment effect we will evaluate the coefficients associated with group and the group by time interaction. Planned contrasts will be constructed from the mixed model to evaluate differential changes in percent weight loss between the two conditions from baseline to post-treatment at 12 and 24 months. This procedure will be utilized for each of the other secondary measures.

An exploratory aim will be to evaluate direct program costs and self reported health care utilization.

Analysis Plan: The overall approach will be to report descriptive statistics, including the following: overall and component specific program costs, including allocation of time expenditures by screening staff and GLB interventionists, and the direct cost of all materials provided. For health care utilization we will summarize the self-reported number of times an individual has visited a physician/health care provider (outpatient), a hospital emergency room, the total number of separate hospital admissions, and the total number of nights spent in the hospital in the previous six months. Comparisons will be made between the two groups (GLB + 10TC and GLB + NC). Summary descriptive statistics will include mean, median, standard deviation and confidence intervals for continuous variables and proportions, ranges and percentiles for categorical variables.

[\[reviewer notes-\]](#)

2.19

Will this research be conducted in (a) a foreign country and/or (b) at a site (e.g., Navajo Nation) where the cultural background of the subject population differs substantially from that of Pittsburgh and its surrounding communities?

* No

Note that copies of training records, licenses, certificates should be maintained in the study regulatory binder and are subject to audit by the Research Conduct and Compliance Office (RCCO).

In addition, individuals planning to conduct human subject research outside the United States must complete an optional module on the CITI training website: International Studies. [Click here](#) to access the instruction sheet for accessing optional CITI modules.

[\[reviewer notes-\]](#)

2.21

Will this research study be conducted within a nursing home located in Pennsylvania?

* No

[\[reviewer notes-\]](#)

Section 3 - Human Subjects

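### The two-level randomisation stratum is modelled as a random effect with no stratum-by-time term, so contrasts on raw repeated measures, and the ≥5% responder test as powered, do not use the stratified randomisation

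*Combined protocol and SAP*

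**What the plan says.** Section 2.3 (design): after the 12-session programme, "participants will be assigned by a stratified block randomization scheme to continued telephone contact" or to newsletter control. "Stratification will be based on the category of percent weight loss achieved during the first phase of intervention", with a cut at 3.5%. Assessments are at 0, 4, 12 and 24 months.

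Section 2.18 (opening paragraph): in the mixed model, "treatment group, time, and time by group interaction are treated as fixed effects". Subject and the weight-loss category are the other terms, and the text says of them: "<3.5% and >3.5%) are treated as a random effects to account for individual subject variability". No stratum-by-time term is listed and no covariance structure is given. A later sentence on regression adjustment lists demographic variables, sessions completed and variables that differ at baseline. It does not list the stratum.

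Section 2.18 (analysis plan for Hypothesis 3): the arms are to be compared by testing the group and group-by-time coefficients of this model. For change from baseline to 12 and 24 months, the section then specifies: "Planned contrasts will be constructed from the mixed model to evaluate differential changes in percent weight loss between the two conditions". The same procedure is to be used for the other measures.

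Section 2.18 (power; the responder part is repeated in 3.12): the primary endpoint is the proportion with ≥5% weight loss at 12 months. Its power rests on a Fisher's exact test with 120 per arm after 25% attrition. No stratified method is named for it.

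**The concern.** A random effect treats its levels as a sample from a larger population. Here the two levels are fixed by design and cover everyone. The stated reason, variability between individuals, fits the subject term but not the stratum.

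The larger issue is what the term does for the treatment comparison. Stratified randomisation balances first-phase weight loss across arms, which lowers the true variance of the treatment difference wherever that factor predicts the outcome. The analysis gains from this only if its standard error also leaves out the between-stratum variance. If it does not, the reported standard error exceeds the true one, the test rejects less often than 5% under the null, and power is lost. First-phase weight loss is likely to predict month-12 weight, so weight outcomes are the ones most exposed.

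**Working it through.** **1. The plan's power figures (120 per arm, two-sided 0.05).** Exact enumeration of Fisher's test gives 0.818 for 33.3% vs 52.3% and 0.798 for 40% vs 59% (stated 80% for 19 points), and 0.887 for 33.3% vs 54.3% (stated 90% for 21 points). For weight with SD 10.5 lb, SE = 10.5 × √(2/120) = 1.356. Power is Φ(3.8/1.356 − 1.96) = 0.800 and Φ(4.4/1.356 − 1.96) = 0.901. The stated figures reproduce. They come from unstratified tests, so this point does not alter them.

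**2. Why a time-constant stratum term cancels.** Write Y(i,t) = μ(t) + β(t)·group + u(stratum) + v(subject) + e(i,t). Then Y(i,12) − Y(i,0) = [μ(12) − μ(0)] + [β(12) − β(0)]·group + e(i,12) − e(i,0). The stratum term u has gone, whether random or fixed. Any stratum difference in *change* stays in the residual unless the model has stratum-by-time.

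**3. Size in a raw-weight model.** Assumptions (none in the documents): 240 people, strata 50:50, residual SD 6 lb, stratum gap of 12 lb × (0, 1, 1, 0.8) at 0, 4, 12 and 24 months.
- The gap pattern has mean 0.7, and its squared deviations sum to 0.49 + 0.09 + 0.09 + 0.01 = 0.68.
- Extra residual variance = (0.68/3) × 12² × 0.25 = 8.16.
- SE without stratum-by-time = √[2 × (36 + 8.16)/60] = 1.213.
- SE with stratum-by-time = √[2 × 36/60] = 1.095.

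REML fits to 200 simulated trials agree: mean SE 1.214 with no stratum term, 1.214 with a fixed main effect, 1.214 with a random intercept, and 1.096 with stratum-by-time. The excess is 1.213/1.095 = 1.11, or 1.214/1.054 = 1.15 against the empirical SD of those 200 trials.

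**4. Size as a function of the correlation.** Assume month-4 percent loss is normal with SD 4 and mean 3.5, split at 3.5, and has correlation r with month-12 change. The stratum then explains R² = (2/π)r² of the month-12 variance. The SE ratio is 1/√(1 − R²) and the type I error is 2Φ(−1.96 × ratio).

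| r | R² | SE ratio | Type I error |
|---|---|---|---|
| 0.50 | 0.159 | 1.09 | 3.3% |
| 0.65 | 0.269 | 1.17 | 2.2% |
| 0.75 | 0.358 | 1.25 | 1.4% |

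Simulation at these correlations, with mean month-4 loss of 3.5% or 5%, gave SEs 8% to 27% too large and type I errors of about 3.5% down to 1.3%. At r = 0.30 the inflation was 0% to 2%.

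**5. Percent change from baseline as the outcome (months 12 and 24).** Assumptions: subject SD 4, residual SD 3, stratum gap 6 points. SE with stratum = √(25/60) = 0.645; without it, √[(25 + 6²/4)/60] = 0.753. REML fits gave 0.645 with random stratum, 0.645 with fixed stratum and 0.751 with none. The random intercept does the whole job here.

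**6. The variance component.** With no true stratum gap, the estimated stratum variance was about zero in 71% of replicates. That shows how little two levels can support, although the contrast SE hardly changed.

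**7. Responder endpoint.** In simulation at r = 0.50 to 0.75, null rejection was 1.6% to 3.5% for Fisher's test and 4.3% to 5.6% for a stratified Cochran–Mantel–Haenszel (CMH) test. Part of that gap is Fisher's own conservatism: by exact enumeration with no stratum effect its size at 120 per arm is 3.3% to 3.9% for common rates of 30% to 50%.

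**The case against.** A reader might infer that the random term leaves the stratification out of every treatment contrast and so makes all the standard errors too large. The documents do not support that. The stratum is named in the model. Hypothesis 3 compares arms on changes in absolute and percent weight loss, and where percent change is the modelled outcome, a random stratum intercept recovers essentially all the precision (step 5).

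Nor is random versus fixed the cause in the raw-weight case. A fixed main effect gives the same inflated SE (step 3); what is missing is stratum-by-time. Replacing random by fixed alone would therefore achieve little.

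A reader might also infer that the trial falls short of its stated power. It does not: the calculation uses unstratified tests and reproduces, so adjustment adds power beyond those figures.

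Three limits also stand. Section 2.18 says random effects without specifying a covariance structure, so a random intercept is the natural reading and no more. The correlations are assumed. Glucose, gait, grip, balance and quality of life are probably less tied to first-phase weight loss, so the gain there is probably smaller.

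What remains is that the plan does not settle how each outcome is coded. Its contrasts run from baseline across repeated assessments and extend to the other measures, so the raw-value model is an open reading, and in it the stratum has no effect on the contrasts.

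**Conclusion.** The point holds in limited form. A two-level design factor should not carry a variance component, and without stratum-by-time the planned model does not use the stratified randomisation for change contrasts on raw repeated measures. The responder endpoint has the same gap, because only an unstratified test is named, and that in the power section.

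For weight, the cost is an SE roughly 8% to 27% too large and a type I error of about 3.5% down to 1.3%. This rests on an assumed month-4/month-12 correlation of 0.50 to 0.75 and on an analysis that does not use the stratum. The error is conservative, with no bias in the treatment estimate. It is absent where percent change is the outcome, and it leaves the stated 80% and 90% power figures intact. It is worth correcting because the correction is nearly free.

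**What to change.** In the opening paragraph of section 2.18, take the weight-loss category out of the random effects. Enter it as a fixed effect, coded as used at randomisation, with a stratum-by-time interaction, and keep only subject-level random or residual terms. State for each outcome whether raw values or change from baseline are modelled. For the ≥5% responder endpoint, name a stratified analysis: a CMH test, or logistic regression with stratum as a covariate.

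The cost is two or three sentences in the analysis plan and a few degrees of freedom in the model. No new data, visits or participants are needed, and the sample size can stay as it is.

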The proposed project is based on the premise that the annual Medicare enrollment period in an institutional context presents an ideal opportunity to reach eligible, high-risk elders. Retired adults, considering their future health care coverage needs, may be particularly receptive to the proposed intervention and employers and insurers providing such benefits may be more likely to offer programs that have been demonstrated to be effective and sustainable. Thus, we propose to implement the GLB 12-session intervention (GLB-12) as part of the annual health benefit package offered to high-risk retirees at a large public university. Participants will be 320 non-diabetic adults, aged 65-80, with a BMI \geq 27 and at least one additional cardio-metabolic risk factor. First, we will evaluate the feasibility of recruiting for and implementing an in-person group program (GLB-12) within this infrastructure. Next, we will conduct a randomized, controlled comparison of two follow up protocols for the remainder of one year of intervention, 8-sessions of continued small group contact by telephone (GLB+8TC; N = 160) or a 2-newsletter control condition (GLB + NC; N = 160). The primary aims are to:

Aim 1: Document that the GLB-12 intervention is feasible and effective when implemented with Medicare enrolled retirees.

Hypothesis 1 (feasibility): We will enroll 107 participants per year, they will complete 65% of sessions, return 50% of self-monitoring records and report above average program satisfaction at the month 4.

Hypothesis 2 (effectiveness): Participants will achieve 5% weight loss and 150 minutes of self reported physical activity per week, and show corresponding waist, glucose, blood pressure and lipid improvements (adjusted for medication use) at month 4.

Aim 2: Evaluate the effects of continued small group contact by telephone (GLB+8TC) compared to a newsletter control condition (GLB+NC) on anthropometric, cardio-metabolic, physical function and health related quality of life (HRQL) measures at 12- and 24-months follow up.

Hypothesis 3: GLB+8TC will be associated with more favorable weight, waist, glucose, lipid, blood pressure gait speed, grip strength, balance and HRQL at month 12 and 24 assessments.

An exploratory aim will be to evaluate direct program costs and self reported health care utilization.

1.3**Background: Briefly describe previous findings or observations that provide the background leading to this proposal.**

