Following GLB-12, group telephone sessions will be the delivery format for the remaining one year of intervention. The content, structure and sequence of these sessions is similar to those conducted in person; however, a group phone coaching script and a participant handout will be developed that details norms and procedures for phone interactions. As with face-to-face intervention, the phone coaching sessions amplify core diabetes prevention and cardiovascular health messages and allow for continued weight, diet, and activity monitoring and accountability. Prior studies have shown that this method of coaching has been employed successfully both for initial standard (core) as well as maintenance interventions with older rural women (44, 45). All participants will be asked to call into a toll-free conference line, and to treat the weekly call time as a standing appointment for which they need to be in a private location free from distractions. Participants will be asked to dedicate a maximum of 45 minutes for actual phone call time, and to utilize 15 minutes post-call time to review home assignments on their own. In the GLB + 8TC condition, the first of the eight continued contact sessions be delivered face to face to orient those randomized to telephone continued care to the specific protocol and procedures, provide a new participant manual and other materials necessary to complete the remainder of the program. Because problem solving strategies will be a dominant focus of these continued contact sessions, we will limit participation on each group phone call to approximately 5-7 individuals. In addition, because of the critical importance of transitioning from face-to-face weekly sessions to home-based self-monitoring during the follow up phase, all GLB +8TC participants will be provided with a digital bathroom scale and a set of post-cards with instructions to mail in (or phone in) their weekly weights and physical activity minutes for the duration of the intervention.

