Analysis Plan: The overall approach will be to report descriptive statistics, including the total number of participants enrolled, the distribution of the number of GLB-12 sessions completed, the percentage of participants completing 8 (65%) or more sessions (the definition for acceptable attendance), the percentage of participants who return six (50%) or more of the self monitoring records (the definition for acceptable behavioral adherence) and the distribution of program satisfaction ratings. Summary descriptive statistics will include mean, median, standard deviation and confidence intervals for continuous variables and proportions, ranges and percentiles for categorical variables.

Hypothesis 2 (effectiveness): On average, participants will achieve $\geq 5\%$ weight loss (the definition of acceptable weight outcome in prevention programs) and ≥ 150 minutes of self reported moderately vigorous physical activity minutes per week (the recommended level in prevention programs), and show corresponding waist, glucose, blood pressure and lipid improvements (adjusted for medication use).

Analysis Plan: For the weight measure, we will examine both absolute weight change (kg) and percent weight change pre to post-intervention (0-4 months). Student t-test and Chi-Square statistics will be used to assess the absolute and percent weight change outcomes, respectively. We will also use descriptive statistics to identify the proportion of total participants achieving $\geq 5\%$ weight loss and the proportion achieving ≥ 150 minutes. Similarly, Student t-tests will also be used to assess pre to post intervention changes in waist, glucose, lipid, and blood pressure measures. Because we know that medications will effect these outcomes we will conduct separate sub-group analyses for lipid endpoints to control for statin use, and for blood pressure endpoints to control for blood pressure medication use.

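### Adjusting the arm comparison for sessions completed may condition on sessions that only the telephone arm is offered

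*Combined protocol and SAP*

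**What the plan says.** - **Section 2.18, general paragraph.** After the primary model and the handling of missing data, the plan adds that "regression modeling will be conducted to adjust for covariates, including demographic variables such as age, race, sex, number of sessions completed", together with any variable found to differ between the arms at baseline. The session count has no phase or time limit.
- **Section 2.3.** "Following implementation of the non-randomized GLB-12, participants will be assigned by a stratified block randomization scheme to continued telephone contact" or to newsletters. GLB-12 is therefore entirely pre-randomisation.
- **Section 1.2.** The two follow-up conditions are "8-sessions of continued small group contact by telephone (GLB+8TC; N = 160) or a 2-newsletter control condition".
- **Section 2.6, telephone arm.** "the first of the eight continued contact sessions be delivered face to face". The protocol thus calls the post-randomisation contacts sessions. The control arm is mailed newsletters and has none.
- **Section 2.18, primary analysis.** "The primary analytic strategy will be a mixed models approach in which treatment group, time, and time by group interaction" are the fixed effects. The Hypothesis 3 plan tests the arm effect through group and group-by-time. Neither mentions sessions.

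**The concern.** A covariate in a between-arm model should be fixed before randomisation. If the session count includes the continued contacts, it can reach 20 (12 + 8) in the telephone arm but only 12 in the control arm, because of assignment. Three things follow.

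1. Arm and covariate are strongly correlated, so precision is lost even when nothing else goes wrong.
2. If people who attend more also lose more weight, the model compares telephone participants with controls who attended more of GLB-12. This biases the result against the telephone arm and can show a false disadvantage when there is no effect.
3. If part of the telephone effect works through attending the calls, the adjustment removes that part.

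The adjusted result could then appear to contradict a sound primary analysis.

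The same sentence has a smaller weakness: further covariates are chosen by looking at baseline differences, so the adjusted model is not fixed until the data are seen.

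**Working it through.** **1. The plan's own figure.** From the power text in 2.18: 120 per arm after 25% attrition, SD 10.5 lb, difference 3.8 lb, two-sided 0.05.

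SE = 10.5 × √(2/120) = 1.36 lb. 3.8/1.36 = 2.80, and Φ(2.80 − 1.96) = 0.80. The stated 80% power reproduces (79.7% with the t distribution).

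**2. Inputs the documents do not give (assumptions).** Each person has an attendance propensity p with mean 0.75, shared across phases. GLB-12 attendance is binomial(12, p). Continued-contact attendance is binomial(8, p) in the telephone arm and 0 in control. Three spreads of p are used: Beta(4.5, 1.5), Beta(2.25, 0.75) and Beta(9, 3). Weight loss per GLB-12 session, b, is 0 to 0.5 lb. Between 0 and 100% of the 3.8 lb acts through continued-contact attendance.

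**3. Formula.** With total sessions T as covariate,

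- adjusted difference = 3.8 − β × D, where D is the arm difference in mean T and β is the pooled within-arm slope of weight loss on T;
- SE = 1.36 × √(1 + D²/(4V)), where V is the pooled within-arm variance of T.

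**4. Middle spread, Beta(4.5, 1.5).**

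- Var(p) = 0.0268 and E[p(1−p)] = 0.1607.
- D = 8 × 0.75 = 6.
- Var(T), control: 12 × 0.1607 + 144 × 0.0268 = 5.79. Telephone: 20 × 0.1607 + 400 × 0.0268 = 13.93. V = 9.86.
- SE = 1.36 × √(1 + 36/39.4) = 1.36 × 1.38 = 1.88. Power for an unbiased 3.8 lb: Φ(3.8/1.88 − 1.96) = 53%.
- Pooled covariance of GLB-12 sessions with T: (5.79 + 5.79 + 96 × 0.0268)/2 = 7.07. So β = b × 7.07/9.86 = 0.717b, and the shift is 6 × 0.717b = 4.30b.
- With no mediation: 2.94 lb at b = 0.2, 2.08 at 0.4 and 1.65 at 0.5.
- With no true effect and b = 0.5: mean estimate −2.15 lb, and rejection Φ(2.15/1.88 − 1.96) ≈ 21%.

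**5. Simulation.** Ordinary least squares, 2,500 trials per effect cell and 6,000 per null cell. The table covers all three spreads and 0 to 100% mediation.

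| Loss per GLB-12 session | Adjusted for all sessions (true 3.8 lb) | Rejection with no true effect |
|---|---|---|
| 0.2 lb | 1.8 to 3.1 lb | 7 to 8% |
| 0.4 lb | 1.0 to 2.1 lb | 14 to 18% |
| 0.5 lb | 0.5 to 1.7 lb | 18 to 24% |

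The SE is 1.7 to 2.1 lb throughout. At slope 0 with no mediation the estimate is unbiased, but power is 45 to 58%. Adjusting for GLB-12 sessions only gives 3.7 to 3.9 lb, SE 1.34 to 1.36, power 78 to 82% and rejection of about 5% in every cell.

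**6. Sensitivity to the attendance model.** If everyone has the same 75% propensity, V = (12 + 20)/2 × 0.1875 = 3.0 and the SE doubles: 1.36 × √(1 + 36/12) = 2.71. A separate simulation gave 2.73.

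**7. The ≥5% weight-loss endpoint, if the same regression is applied to it.** Logistic model, standardised risk difference, 33% against 52%, middle spread. Adjusting for all sessions gives 10 to 16 points at 0.2 lb and 7 to 12 points at 0.4 lb. Adjusting for GLB-12 sessions only gives about 19 points.

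**The case against.** The strongest reply is that this is an ambiguity and not a demonstrated error. The neighbouring covariates are demographic or measured at baseline. The Hypothesis 1 text that follows uses the bare word for GLB-12, as in "the percentage of participants completing 8 (65%) or more sessions". The regression is one closing sentence that names no outcome or time point, and the primary model and planned contrasts do not depend on it. Attendance spread, slopes and mediation are assumed, and the results move with them. The plan also does not say the regression will be applied to the ≥5% endpoint.

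Most of this stands, and it limits the weight of the point. It does not settle the meaning. The sentence closes a paragraph in which "we anticipate 75% adherence over the 12-month intervention period" and in which "Those who drop out or are lost to follow-up will be compared to those who have completed intervention sessions and research assessments". Neither phrase is confined to GLB-12, although neither defines the covariate. Where the Hypothesis 1 plan means GLB-12 it can say so, and this sentence does not. An analyst could build either variable, and the two give different answers. The loss of precision needs no assumption about slope or mediation.

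Section 2.18 labels the telephone arm with ten contacts where the design sections say eight, and these should be reconciled. All figures here use eight. With ten, the step 4 shift grows: at 0.4 lb with no mediation the estimate is about 1.8 lb instead of 2.1.

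**Conclusion.** The concern holds as a defect of specification in the covariate-adjusted regression only. As worded, the covariate admits sessions that exist after randomisation in one arm only, and a model built that way does not estimate the effect of assignment. If those sessions are counted, a true 3.8 lb difference appears as roughly 0.5 to 3.1 lb for slopes of 0.2 to 0.5 lb per session, and null rejection reaches 7 to 24%. Even with no bias, power falls from about 80% to 45 to 58%. These sizes rest on the assumed 75% attendance, shared propensity, slopes and mediation shares, and are illustrations of scale. If only GLB-12 sessions were meant, there is no harm, and the change simply records it. The primary mixed model, the Hypothesis 3 contrasts and the power figures are unaffected. The wording should be corrected.

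**What to change.** In section 2.18:

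- Replace the session covariate in between-arm models with the number of GLB-12 sessions completed before randomisation, or drop it.
- Report continued-contact attendance descriptively within the telephone arm. Label any model that uses it as exploratory and not an estimate of the randomised effect.
- Replace selection by observed baseline differences with a short prespecified list of pre-randomisation variables: for example age, sex, race, randomisation stratum, and the baseline value of the outcome where it is not already part of the response vector.
- State that this regression supports the primary mixed model.

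The cost is one or two sentences. GLB-12 attendance is already recorded (section 2.6), so no new data are needed.
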